6.2.3.2. Mixed Model for Repeated Measures Analysis

MMRM analysis will be utilized to estimate the mean change from baseline in the weekly number of CH attacks during the 4-week period after administration of the first dose of the IMP.

Postbaseline data will include data from four 1-week analysis windows derived using the algorithm described in Section 6.1.3. Missing data will be handled as described in Section 6.1.4.3

The MMRM will include baseline preventive medication use (yes or no), gender, region (US/Canada or other), treatment, week (weeks 1 to 4), and week-by-treatment interaction as fixed effects and baseline number of CH attacks as a covariate. The unstructured covariance structure (UN) will be used to model intra-subject correlation. LS mean and SE for each treatment group, LS means and corresponding 95% confidence intervals for the treatment differences (fremanezumab - placebo), and the associated p-values from the overall results for treatment comparisons on the average of weeks 1 to 4 will be presented to support the primary analysis.

Notes: if UN dose not converge, the hierarchy uses the first-order autoregressive structure [AR-(1)] and the compound-symmetry structure (CS).

[REDACTED]

The analysis will be performed on the FAS.

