1. INTRODUCTION AND BACKGROUND INFORMATION

1.1. Introduction

1.1.1. Cluster Headache

Cluster headache (CH) is a primary headache disorder characterized by repetitive attacks of excruciating unilateral head pain and associated with cranial autonomic features (such as lacrimation, conjunctival injection, nasal congestion, nasal rhinorrhea, and partial Horner's syndrome) (Rozen 2005). CH attacks last up to 180 minutes and occur from once every other day to 8 times a day. Cluster periods usually last a few months (typically 3 months) followed by remission periods of months to years (Headache Classification Committee of the International Headache Society [IHS] 2013). A unique feature of CH is the circadian and circannual periodicity nature of the headache attacks. Peak time periods for daily CH onset are 0100 to 0200, 1300 to 1500, and after 2100, with night awakening attacks being more severe than those occurring during the day (Rozen 2005). Some patients tend to have seasonal attacks related to the duration of the photoperiod, with the highest incidence of attacks occurring in January or July with possible relation to solstices or equinoxes (Kudrow 1987).

There are 2 forms of CH: episodic cluster headache (ECH), which is the most common form, where distinct pain-free periods lasting at least 1 month are evident, and chronic cluster headache (CCH) occurring for more than 1 year without remission or with remission periods lasting less than 1 month. About 10% to 15% of patients with CH have the CCH form (Headache Classification Committee of the IHS 2013).

The pathophysiology of CH is complex and not fully understood. Current theories implicate mechanisms such as vascular dilation, trigeminal nerve stimulation, and circadian effects. Histamine release, an increase in mast cells, genetic factors, and autonomic nervous system activation may also contribute (Weaver-Agostoni 2013). However, 3 major features of CH are the main focus for understanding its pathophysiological model: trigeminal distribution of the pain (including association with neuropeptide level changes), ipsilateral cranial autonomic features, and (circadian) episodic pattern of attacks (May 2005).

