2.1.1. Justification of Primary Endpoint

For patients with ECH, headache attacks may happen in distinct periods of time, often seasonally (occur daily for some weeks [7 days to a year [if not treated]]) followed by a period of remission with distinct pain-free periods lasting at least 1 month (often last for months to years). On average, a cluster period lasts 6 to 12 weeks, and remissions can last up to 12 months. The duration of pain in these patients supports the need to evaluate time point of the primary endpoint of 4 weeks. This short duration of assessment at 4 weeks in patients with ECH should capture the seasonality nature and the possibility of prolonged remission.

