4.1. Patient Inclusion Criteria

Patients may be randomized/enrolled in this study only if they meet all of the following criteria:

- a. Patients are capable of giving signed informed consent as described in [Appendix D](#) which includes compliance with the requirements and restrictions listed in the informed consent form (ICF) and in this protocol.
- b. The patient is a man or woman 18 to 70 years of age, inclusive.
- c. The patient has a history of ECH according to ICHD-3 beta criteria ([Headache Classification Committee of the IHS 2013](#)) for ≥ 12 months prior to screening including the following:
 - Attacks of severe, strictly unilateral pain which is orbital, supraorbital, temporal or in any combination of these sites, lasting 15 to 180 minutes and occurring from once daily every other day to 8 times a day for more than half of the time when the disorder is active.
 - The pain is associated with at least 1 of the following symptoms or signs: ipsilateral conjunctival injection, lacrimation, nasal congestion, rhinorrhea, forehead and facial sweating, miosis and/or ptosis and/or eyelid edema, and/or sense of restlessness or agitation.
 - CH attacks occurring in periods lasting from 7 days to 1 year, separated by pain-free periods lasting at least 1 month.
- d. CH attacks of a new cluster cycle have started within ≤ 2 weeks (14 days, inclusive) prior to screening and, based on the patient's previous medical history, it is expected that the patient's CH attacks will continue for ≥ 6 weeks after the screening visit.
- e. The patient has a total body weight of ≥ 45 kg
- f. The patient is not using or using ≤ 2 concomitant medications that are commonly prescribed as preventive treatments for CH ([Appendix H](#)), regardless of the indication for which the medication was prescribed. Patients must be on a stable dose and regimen for at least 2 weeks prior to screening and throughout the study.
- g. If a patient is receiving Botox, it should be in a stable dose regimen, considered as having ≥ 2 cycles of Botox prior to screening. The patient should not receive Botox during the run-in period up to the evaluation period (4 weeks) where the primary endpoint is evaluated.
- h. The patient has demonstrated compliance with the electronic headache diary during the run-in period by entry of headache data on 85% of days during the run-in period.

- i. The patient has at least 7 CH attacks during the run-in period.

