6.3.2. Mean Change from Baseline in the Number of Cluster Headache Attacks

The following 2nd and 3rd secondary efficacy endpoints will be analyzed using an MMRM method in a manner analogous to the analysis as described in Section 6.2.3.2 with month and month-by-treatment interaction in the model instead.

- the mean change from baseline (run-in period) in the number of CH attacks during the 12-week period after administration of the first dose of the IMP, ie, based on week 0 to 12 data
- the mean change from baseline (run-in period) in the number of CH attacks during the 4-week period after administration of the third dose of the IMP, ie, based on week 8 to 12 data

Postbaseline data will include data from three 4-week analysis windows (weeks 1 to 4, weeks 5 to 8, and weeks 9 to 12) derived using the algorithm described in Section 6.1.3. CH attacks within each analysis window will be derived from the e-diary data as described in Section 6.1.1. The weekly average of number of CH attacks for a patient in each analysis window will be calculated and prorated to 7 days using formula [1]. Missing data handling methods are provided in Section 6.1.4.2.

The analysis will be based on data from all three 4-week analysis windows. Results for each endpoint will be subsetted from PROC MIXED outputs. For the 2nd secondary endpoint, the overall results will be presented; for the 3rd secondary endpoint, the results from the weeks 9 to 12 analysis window will be presented.

6.3.3. Mean Change from Baseline in the Weekly Average Number of Days with Use of Cluster-Specific Acute Headache Medications (Triptans and Ergot Compounds) During the 12-Week Period After Administration of the First Dose of the IMP

Use of triptans and ergot compounds for CH will be recorded in the e-diary. The 12-week period is the period from administration of the first dose of the IMP to the EOT/early withdrawal visit. The weekly average number of days with use of triptans or/and ergots for CH for a patient during 12-week period will be calculated and prorated to 7 days using formula [1]. Missing data handling method is provided in Section 6.1.4.2.

Data will be analyzed using an ANCOVA method in a manner analogous to the primary endpoint as described in Section 6.2.2.

MMRM analysis will be based on weekly analysis windows. Data in weekly analysis windows will be derived.

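### The MMRM for the 12-week and weeks 9–12 secondary endpoints fits one baseline slope to all three windows; a baseline-by-month term could recover modest precision at almost no cost

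*SAP*

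**What the plan says.** SAP 6.2.3.2 lists the terms of the repeated-measures model in prose. Treatment interacts with time, but baseline enters once: "week-by-treatment interaction as fixed effects and baseline number of CH attacks as a covariate". On covariance it says: "The unstructured covariance structure (UN) will be used to model intra-subject correlation".

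SAP 6.3.2 applies this model to the second and third secondary endpoints "with month and month-by-treatment interaction in the model instead". The data are as follows: "Postbaseline data will include data from three 4-week analysis windows (weeks 1 to 4, weeks 5 to 8, and weeks 9 to 12". The second secondary endpoint is read from the overall result. For the other, "for the 3rd secondary endpoint, the results from the weeks 9 to 12 analysis window will be presented". No baseline-by-month term is mentioned. A block of 6.2.3.2 is redacted, so this reading rests on the prose and not on the model code.

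On the course of the disease, Protocol 2.1.1 says: "On average, a cluster period lasts 6 to 12 weeks, and remissions can last up to 12 months". Protocol 1.1.1 gives a longer figure: "Cluster periods usually last a few months (typically 3 months) followed by remission periods of months to years". Protocol 4.1 sets entry early in the cycle: "CH attacks of a new cluster cycle have started within ≤ 2 weeks (14 days, inclusive) prior to screening". It asks only that attacks be expected to continue for at least six weeks after screening.

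**The concern.** The outcome is change from baseline. While a patient is in cycle, the later attack count tracks the baseline count. Once the cycle has ended, the count is near zero and the change is close to minus the baseline. If many cycles end during follow-up, the slope of change on baseline steepens towards −1 from window to window. A single slope then misfits at least one window, and the misfit goes into the residual covariance and widens the treatment contrast.

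What is at stake is precision on two formal secondary endpoints. The protocol synopsis places the secondary endpoints under multiplicity control. The Amendment 02 wording in Protocol 16.1 tests them in sequence and stops at the first failure (the current Section 9.6 is redacted). If that wording still applies, a near miss here would also block the acute-medication, oxygen and PPSI claims.

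**Working it through.** **The plan's own figure.** Protocol 9.1 uses a difference of 1, SD 2 and two-sided alpha 0.05. Then n = 2 × (1.96 + 1.2816)² × 2² / 1² = 84.1, so 85 per arm. At 86 per arm, 1 / (2 × √(2/86)) = 3.279, and power = Φ(3.279 − 1.96) = 0.906. Also 258 / 0.86 = 300. The figure reproduces. It belongs to the primary endpoint; the documents state no power for the MMRM endpoints.

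**Timing.** Onset is 0–14 days before screening and the run-in is 7–10 days, so the first dose falls 7–24 days after onset. Weeks 9–12 run from 8 to 12 weeks after the first dose, which is roughly 9 to 15 weeks after onset. Both stated cluster durations (6 to 12 weeks, and typically 3 months) put many cycle ends before or inside that window.

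**Direction of the slope.** These inputs are assumptions, because the documents give none: patient rates with mean 10 per week and SD 4, Poisson counts, and a 7-day baseline. The reliability of baseline is r = 16 / (16 + 10) = 0.615. If p is the expected share of a window spent in cycle, and p does not depend on the rate, the slope of change on baseline is r × p − 1. Take cycle length as uniform on 6–12 weeks from onset, and the first dose at 7 + 8.5 = 15.5 days (2.2 weeks) after onset:

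| Window | Weeks after onset | p | r × p − 1 | Simulated slope |
|---|---|---|---|---|
| Weeks 1–4 | 2.2–6.2 | 1.00 | −0.38 | −0.38 |
| Weeks 5–8 | 6.2–10.2 | (2 + 1.8)/6 = 0.633 | −0.61 | −0.59 |
| Weeks 9–12 | 10.2–14.2 | (1.8²/2)/(4 × 6) = 0.068 | −0.96 | −0.94 |

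The hand calculation ignores the entry rule of at least 7 run-in attacks; the simulation applies it. The simulated common slope is −0.81. It sits near the weeks 9–12 slope because that window has the smallest residual variance and so carries most weight. With longer cycles the weeks 9–12 slope is less steep, about −0.61 in one run.

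**Effect on variance, by formula.** Let b be the vector of window slopes, c the common slope, S the residual covariance and s the baseline SD. Fitting one slope replaces S by S + s²(b − c)(b − c)′. With level slopes 0.8, 0.5 and 0.2 and equal baseline and residual SD, c = 0.5. The weeks 9–12 variance ratio is 1 + 0.3² = 1.09, an SE ratio of 1.044. For the 12-week average the misfits cancel (0.3 + 0 − 0.3 = 0) and the ratio is 1.000. They stop cancelling when residual SD differs by window: the 12-week SE ratio was then 1.00–1.22 and the weeks 9–12 ratio 1.00–1.16. Baseline SD two to three times the residual SD gave weeks 9–12 SE ratios of 1.08–1.80.

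**Effect on variance, by simulation.** Rate 10 per week (SD 4), Poisson counts, 86 per arm, unstructured covariance, no dropout. Entries are the variance with a common slope divided by the variance with separate slopes, covering empirical and model-based values:

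| Assumed cycle length | Trials | Weeks 9–12 | 12-week average |
|---|---|---|---|
| 6–12 weeks from onset | 800 | 1.07–1.08 | 1.10–1.11 |
| 6–12 weeks from onset | 300 | see note | 1.09–1.15 |
| Same, at least 6 weeks left after screening | 300 | see note | 1.06–1.11 |
| 6–12 weeks from screening | 800 | 1.10–1.11 | 1.01 |
| 6–12 weeks from randomization | 300 | see note | 1.00 |
| 8–14 weeks | 800 | 1.07–1.09 | not tabulated |
| Up to 16 weeks | 800 | 1.02–1.06 | 1.00–1.01 |
| 6–16 weeks from onset, at least 6 weeks left | 300 | see note | 1.01–1.02 |
| 10–16 weeks from onset | 300 | see note | 1.00–1.01 |

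Note: across the 300-trial rows the weeks 9–12 ratio was 1.01–1.11.

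**In terms of power.** If separate slopes gave 90.6% power (illustrative only), the common slope would give Φ(3.279/ratio − 1.96), where ratio is the SE ratio. For variance ratios of 1.02, 1.11 and 1.15 this is 0.901, 0.875 and 0.864.

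**Validity and cost.** These come from 1,500 simulated trials per scenario, 100 per arm, with 15–18% dropout. When dropout was random, or depended on baseline equally in all arms, no bias appeared and type I error was 0.04–0.06. When dropout depended on baseline in opposite directions by arm, a deliberately extreme case, the common-slope contrast was biased by −0.45 attacks per week at weeks 9–12 (type I error 0.113) and by −0.19 on the 12-week average (0.082). With the interaction, type I error was 0.055 and 0.054. When slopes are truly equal, the interaction leaves the weeks 9–12 SE at 0.602 against 0.601 (SD 4), and rejection rates at 0.899 in both models (SD 2).

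**The case against.** The specified model is a recognised MMRM. Randomization keeps the treatment contrast unbiased whether or not the baseline slope is right. The premise that baseline loses predictive value is nowhere quantified in the documents. If clusters typically last three months, as Protocol 1.1.1 says, many patients are still in cycle late in follow-up and little is lost. All of this stands. It makes the point one of efficiency, conditional on cycle length.

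Three stronger readings are tempting, and the documents do not support them.

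- A reader might infer that the estimates are biased whenever dropout depends on baseline. That is not enough. Bias appeared only when the dependence differed by arm, and nothing in the documents suggests that it would.
- A reader might take the poor fit in weeks 1–4, where the simulated variance loss was about 36–42%, as the size of the problem. SAP 6.3.2 reports no weeks 1–4 result from this model, and the primary endpoint is a single-window ANCOVA (Protocol 9.5.4.1).
- A reader might want the same change in the 6.2.3.2 sensitivity analysis. That model covers weeks 1–4 only. Week 4 ends 35–38 days after screening, about 5.0–5.4 weeks, inside the six weeks for which attacks are expected to continue. The end of cycles gives little reason for slope drift there.

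**Conclusion.** The point holds as a low-cost improvement. On the prose of SAP 6.2.3.2 and 6.3.2, one baseline slope is imposed on three windows between which the slope plausibly changes. Under the assumed attack rates, the variance of the treatment contrast is larger by about 2–11% for weeks 9–12 (SE about 1–5%, since √1.02 = 1.01 and √1.11 = 1.05). For the 12-week average it is larger by about 0–15% (SE up to about 7%, since √1.15 = 1.07), and close to zero if cycles last up to 16 weeks.

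These sizes rest on an assumed 10 attacks per week (SD 4), Poisson counts and the cycle-length ranges shown. The documents supply only the cluster durations, the entry rule and the sample size. Inference stays valid under non-differential dropout, and no endpoint is invalidated.

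**What to change.** Pre-specify, before unblinding, a baseline-by-month interaction in the SAP 6.3.2 MMRM for the second and third secondary endpoints, and keep everything else in that model. With three windows this adds two fixed-effect parameters in about 258 patients, with no visible loss if the slopes prove equal. A matching baseline-by-week term in the 6.2.3.2 sensitivity model is optional. If the redacted code already contains the interaction, it is enough to state it in the prose.

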9.1. Sample Size and Power Considerations

A sample size of 258 patients (86 evaluable patients completing the study per treatment group) will provide at least 90% power to detect a treatment difference of 1 CH attack in the weekly average (assuming a common standard deviation [SD] of 2 CH attacks) at a 2-sided alpha level of 0.05. Assuming a 14% discontinuation rate, approximately 300 patients will be randomized in the trial.

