6.3. Secondary Efficacy Endpoints and Analyses

The secondary efficacy endpoints are listed in Section 1.2. Analyses will be based on the FAS and PP analysis sets [REDACTED].

As exploratory analyses, endpoints analyzed using an ANCOVA method will be also analyzed using MMRM method in a manner analogous to the analysis as described in Section 6.2.3.2. The analysis windows will be specified in the related section.

6.3.1. Proportion of Patients with a $\geq 50\%$ Reduction from Baseline in the Weekly Average Number of CH Attacks During the 4-Week Period After the First Dose of the IMP

This secondary efficacy endpoint will be analyzed using Cochran-Mantel-Haenszel (CMH) test stratified by baseline preventive medication use (yes or no). Descriptive statistics (count and percent) and p-value for Row Mean Scores difference will be presented.

CH attacks will be derived from the e-diary data as described in Section 6.1.1. The analysis will be based on weeks 1 to 4 analysis window which will be derived using the algorithm described in Section 6.1.3. The weekly average number of CH attacks will be calculated based on data available and prorated to 7 days using formula [1]. Missing data handling methods are provided in Section 6.1.4.2.

The proportion of reduction for a patient will be calculated using formula [2]. Responders will be those with $\geq 50\%$ reduction.

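### If the unstructured covariance does not converge, the SAP's MMRM falls back to AR(1), and the readable text names no robust standard error; in the exploratory 12-week weekly models the 5% error could then be about 8–21%

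*SAP*

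**What the plan says.** SAP 6.2.3.2 describes a sensitivity MMRM on four weekly windows, with UN as the covariance. The note on non-convergence reads: "the hierarchy uses the first-order autoregressive structure [AR-(1)] and the compound-symmetry structure (CS"). No heterogeneous structure, empirical standard error or degrees-of-freedom method appears in the readable text. The block directly after the note is redacted.

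The rule is reused in three places:

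- **SAP 6.3**, as exploratory work: "endpoints analyzed using an ANCOVA method will be also analyzed using MMRM method in a manner analogous to the analysis as described in Section 6.2.3.2".
- **SAP 6.3.3 and 6.3.4** (triptan/ergot days, oxygen days): "MMRM analysis will be based on weekly analysis windows". The period is 12 weeks, so there are 12 windows. The main analysis of both endpoints is an ANCOVA on one value per patient.
- **SAP 6.3.2**: an analogous MMRM on three 4-week windows is the main analysis of the second secondary endpoint (12-week average) and the third (weeks 9–12). The protocol synopsis places the secondary endpoints under Hochberg control.

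**The concern.** UN allows any pattern of variances and correlations. AR(1) allows one variance and a correlation of ρ to the power of the lag. At lag 11 that is 0.5^11 = 0.0005 for ρ = 0.5, or 0.9^11 = 0.31 for ρ = 0.9.

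Protocol 2.1.1 puts an average cluster period at 6 to 12 weeks, and inclusion criterion d admits patients within 14 days of cycle onset. Many cycles will therefore end during the 12 weeks. Patients will differ persistently in attack rate and in when their cycle stops, so distant weeks can stay correlated and the spread can change over time. AR(1) represents neither. Its model-based standard error then understates the variance of a patient's average over windows, giving intervals that are too narrow and p-values that are too small.

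CS stands after AR(1) in the sequence. AR(1) has only two parameters and will nearly always converge, so CS will rarely be reached.

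**Working it through.** **1. Plan's own figures.** Protocol 9.1 gives "A sample size of 258 patients (86 evaluable patients completing the study per treatment group"), "a treatment difference of 1 CH attack in the weekly average", "assuming a common standard deviation [SD] of 2 CH attacks" and "at a 2-sided alpha level of 0.05". With 86 per arm, SE = 2 × √(2/86) = 0.305 and power = Φ(1/0.305 − 1.96) = 90.6%. Also 258/0.86 = 300. The stated size is reproduced. It fixes the number per arm but says nothing about within-patient correlation, so every correlation below is an assumption.

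**2. UN parameters,** m(m+1)/2: 6 for 3 windows, 10 for 4 and 78 for 12.

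**3. Formula.** With complete data and a saturated treatment-by-window mean, the treatment difference averaged over m windows is the difference in patient means. Let S be the true covariance, V the AR(1) matrix minimising log|V| + tr(V⁻¹S), and c = 1/m in each position. Then

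error rate = 2 × [1 − Φ(1.96 × √(c′Vc / c′Sc))].

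**4. Worked case,** true correlation constant at 0.5, fitted AR(1) ρ = 0.5:

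- m = 12: c′Sc = (1 + 11 × 0.5)/12 = 0.542; c′Vc = 32.0/144 = 0.222; √(0.222/0.542) = 0.640; error 20.9%.
- m = 4: c′Sc = 2.5/4 = 0.625; c′Vc = 8.25/16 = 0.516; error 7.5%.
- m = 3: c′Sc = 2/3 = 0.667; c′Vc = 5.5/9 = 0.611; error 6.1%.

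**5. Error rate (%) for the average over windows, AR(1) with model-based SE:**

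| Assumed true pattern | 12 windows | 4 windows | 3 windows |
|---|---|---|---|
| Constant 0.2 | 18.7 | 7.2 | 6.0 |
| Constant 0.3 | 21.1 | 7.6 | 6.1 |
| Constant 0.4 | 21.6 | 7.7 | 6.1 |
| Constant 0.5 | 20.9 | 7.5 | 6.1 |
| Constant 0.7 | 16.4 | 6.7 | 5.7 |
| Constant 0.9 | 8.8 | 5.6 | 5.3 |
| Stable patient effect plus AR(1) | 6.6–14.3 | 5.1–6.1 | 5.1–5.4 |
| AR(1) plus measurement noise | 8.8–16.8 | 5.8–7.0 | 5.4–5.9 |
| True AR(1) | 5.0 | 5.0 | 5.0 |

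An assumed process for medication days, bounded at 0 to 7 per week, gave 8–10% with 12 windows.

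**6. Finite-sample check.** REML AR(1) fits, three arms of 86, 2,000 trials per setting, no covariates or dropout. With 12 windows and constant correlation 0.3/0.5/0.7/0.8 the rates were 20.4/21.7/16.8/13.6%. With 4 windows they were 6.6–7.5%, and with 3 windows 5.4–6.7%. Using the variance of each patient's own mean instead of AR(1), the rate was 3.8–5.7% in all 12 settings.

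**7. Weeks 9–12 contrast, 3 windows.** Here the common variance matters.

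- If the SD rises as 1, 1.5, 2, CS fits the average variance (1 + 2.25 + 4)/3 = 2.417 against a true 4 in the last window. √(2.417/4) = 0.777, so the error is about 12.8%; AR(1) gives 12.5–12.7%.
- If the SD falls as 1, 0.75, 0.5, the ratio is 0.604/0.25 = 2.417 and the error is 0.2%; AR(1) also gives 0.2%.
- In an assumed attack-count process (mean 9 per week before the at-least-7 cut, exponential remaining cycle), AR(1) gave 2%, 5% and 7.5% for mean remaining cycles of 5, 8 and 12 weeks.

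**The case against.** A reader might infer that the plan omits a robust standard error. The documents do not support that: redacted text follows the note directly, and an empirical option could be there.

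A reader might also infer that a confirmatory result is exposed to 8–21% error. It is not. That range belongs to MMRMs that SAP 6.3 labels exploratory, on endpoints whose main analysis is an ANCOVA with no repeated-measures covariance. In 6.2.3.2 itself there are four windows and the range is about 5–8%. The MMRM-based secondary endpoints use three.

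Other fair points:

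- The problem needs UN to fail, and the documents give no probability of that.
- The upper end needs nearly constant correlation over 12 weeks.
- Models of attack counts do not describe days per week of medication or oxygen use. The bounded-days process answers this in part, at 8–10%.
- The checks use complete data, while Protocol 9.1 expects 14% discontinuation.
- CS is already in the sequence and gives 5.0% for the average over windows with complete data.

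These points limit the size of the concern but do not remove it. AR(1) ahead of CS is visible whatever the redaction hides. Moving CS first would repair the average but not the weeks 9–12 contrast, because CS also assumes a common variance. The fallback rule exists precisely for the case where UN fails, and choosing a structure or standard error after unblinding would be post hoc.

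**Conclusion.** The concern holds as a minor, conditional point. If UN fails and the fallback is used with model-based standard errors, the nominal two-sided 5% error is:

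- about 8–21% in the exploratory 12-window MMRMs for triptan/ergot and oxygen days. It is somewhat lower for some mixed patterns and 5% if AR(1) is true;
- about 5–8% in the 4-week sensitivity MMRM;
- about 5–6% for the 12-week average of the second secondary endpoint;
- too low or too high for the weeks 9–12 endpoint, depending on how the variance changes over time.

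This rests on assumed correlation patterns and complete data. With about 258 evaluable patients, failure of UN is unlikely at 6 or 10 parameters and plausible at 78; that is a judgement, not a figure from the documents. The primary ANCOVA and the ANCOVAs for medication and oxygen days are untouched.

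**What to change.** In SAP 6.2.3.2, and wherever it is reused (6.3.2 to 6.3.4), replace the fallback with:

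*If UN does not converge, use heterogeneous Toeplitz, then heterogeneous compound symmetry. For any structure other than UN, base standard errors, confidence intervals and p-values on the empirical (sandwich) estimator clustered on patient.*

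State the degrees-of-freedom method as well. At minimum, keep AR(1)/CS and add the sandwich estimator. If the redacted code already has it, say so in the text.

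The cost is a sentence or two in the SAP and a small code change. Kenward-Roger degrees of freedom cannot be combined with the classical sandwich estimator, which matters little at about 86 per arm. Intervals will usually be wider when the fallback is used. The sandwich does not correct bias from a misspecified covariance when data are not missing completely at random, which is why the richer structures should be tried first.
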